## **Study Protocol**

Ethical approvals from Ulster Research Governance, REC NI and SEHSCT were obtained. The data collection for this cross-sectional study was conducted at the Cardiology department of Ulster hospital between July 2024 to July 2025.

### **Study population and recruitment process:**

Medical records of patients with suspicion for heart failure with preserved ejection fraction were screened by the Staff Grade Cardiology Registrar (direct healthcare team) under the supervision of the Principal Investigator, [name] (Cardiologist) at the participating site (Ulster Hospital, Dundonald). This screening was based on the following inclusion and exclusion criteria.

#### **Inclusion Criteria**

- Males and females
- Age ranged between 18 – 80 years.
- Clinical suspicion of heart failure with preserved ejection fraction
- Ejection Fraction of  $\geq 50\%$  on the most recent Echocardiogram
- Ability to undertake leg exercise without any impediment

#### **Exclusion Criteria**

- Ejection fraction  $< 50\%$  on echocardiogram
- Hospital admission in the past 6 months
- Female subjects that are knowingly pregnant or believe they may be pregnant
- Contra-indication of CPET: myocardial infarction, unstable angina, uncontrolled arrhythmias, moderate to severe valvular stenosis, acute infection, acute endocarditis and history of syncope.

[figure not shown]
#### **Recruitment and informed consent -**

The screened patients were contacted via phone call by the member of the direct healthcare team, informing them about the research project, seeking their verbal consent to receive patient information sheet (PIS). The participant information sheet (PIS) (Annex-1) was posted out to these patients containing information related to the investigation, the conduct of the test, potential risks and benefits, and potential of identifying new undiagnosed condition.

The contact details and past medical history of the patients were shared with the external research team (PhD researcher, Ulster University). The transfer of data took place using secured, password protected organizational email ID.

These patients were given a period of 5 days (cooling off period) to read through the PIS and decide whether they would like to volunteer for the study or not. After 5 days, these patients were contacted via phone call by the PhD researcher and those agreeing to participate in the study were scheduled for an appointment to the hospital. The pre-requisites of the exercise test are re-stated verbally, that includes avoiding strenuous exercise, tea, coffee, smoking and alcohol on the day. The participants are advised to take regular medications for the day and wear appropriate clothing (i.e loose fitted clothes and running shoes).

### **CPET Testing Protocol**

The testing protocol was divided into 5 phases: spirometry, CPET preparation, resting baseline, warm-up, increasing the workload, and recovery.

#### **i- Spirometry:**

The assessment involved measurements of forced expiratory volume in the first second (FEV1), forced vital capacity (FVC) and their ratio (FEV1/FVC). These measures help identify any pre-existing respiratory limitations that could influence CPET results. The CPET software system automatically calculates the maximum voluntary ventilation (MVV) using the FEV1 value from the spirometry using the formula  $MVV = FEV1 \times 40$ . The MVV calculated is used as a reference for respiratory reserve during CPET.

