## **Statistical Plan**

Data was analyzed using SPSSv29. Continuous variables were assessed for normality using the Shapiro-Wilk test and visual inspection of histograms and Q-Q plots. Normally distributed continuous variables are presented as mean  $\pm$  standard deviation (SD), while non-normally distributed variables are presented as median (interquartile range). Categorical variables are presented as frequencies and percentages.

For normally distributed continuous variables, independent samples t-tests were used to compare differences between two groups. For non-normally distributed continuous variables, the Mann-Whitney U test was applied. Categorical variables were analyzed using chi-square tests.

Relationships between continuous variables were examined using Pearson's correlation coefficient for normally distributed variables and Spearman's rank correlation for non-normally distributed variables. Statistical significance was set at  $p<0.05$  for all tests.

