#### Purpose

- To find out how patients with heart related problems respond to an exercise test.
- To understand the heart condition, causes of the symptoms and possible management directions.

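### Respiratory limitation is measured because it can affect CPET results, but no listed analysis can account for it in the two-group comparisons

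*Combined protocol and SAP*

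**What the plan says.** The spirometry subsection of the CPET Testing Protocol has each patient's FEV1, FVC and FEV1/FVC measured before exercise, for this reason: "These measures help identify any pre-existing respiratory limitations that could influence CPET results". The software multiplies FEV1 by 40 to obtain MVV, and one use is given for it: "The MVV calculated is used as a reference for respiratory reserve during CPET".

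The Inclusion Criteria admit patients on clinical suspicion of heart failure with preserved ejection fraction. The Exclusion Criteria name no chronic lung disease and no spirometry threshold. The post-CPET workflow section has peak values, ventilatory thresholds and slopes confirmed by hand, and mentions no spirometry or breathing-reserve step.

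The Statistical Plan then gives four kinds of analysis:
- a t-test where the data look normal: "independent samples t-tests were used to compare differences between two groups";
- a Mann-Whitney test where they do not;
- a chi-square test for categorical data;
- a correlation between pairs of continuous measures, by Pearson's or Spearman's coefficient according to their distribution.

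It names no groups, outcomes or covariates. It has no adjusted model, stratified analysis, analysis-set exclusion or sensitivity analysis.

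**The concern.** The protocol itself identifies a factor that can change the test result, measures it in every patient and lets affected patients enrol. The analysis then has no step that could deal with it. A patient whose exercise is limited by the lungs would not be distinguished from one limited by the heart when peak values or slopes are compared between groups.

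What is at stake is how a group difference is read. If respiratory limitation is unevenly spread, part of any observed difference in a CPET measure, or part of its absence, reflects the lungs rather than whatever defines the groups. The lay Purpose text in the appendices includes this aim: "To understand the heart condition, causes of the symptoms and possible management directions". Separating respiratory from cardiac limitation bears directly on it.

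**Working it through.** The plan states no sample size, effect size, SD or frequency of lung disease, so there is no figure of its own to reproduce. The check is a reading of the text followed by an illustration.

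**1. Can the factor be present?** Yes. Entry is on clinical suspicion, and lung disease is not excluded.

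**2. Can any listed method remove its effect?** A t-test, Mann-Whitney or chi-square test compares two groups on one variable. A Pearson or Spearman coefficient relates two variables. If FEV1 or FEV1/FVC were among the unnamed variables, these methods would describe lung function by group or its association with a CPET measure. None gives a group difference in a CPET measure with lung function held fixed.

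**3. Size of the bias.** Let L = 1 for a patient with respiratory limitation, with frequency p1 in one group and p0 in the other. Let d be the shift that limitation causes in a CPET measure, in SD units among patients alike in group and limitation. With a true group difference δ:

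expected unadjusted difference = δ + d × (p1 − p0)

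so bias = d × (p1 − p0).

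Assumed inputs, none from the documents: p1 of 30 to 40%, p0 of 10 to 15%, d of 0.5 to 0.8.
- Smallest imbalance: 0.30 − 0.15 = 0.15. Largest: 0.40 − 0.10 = 0.30.
- Smallest bias: 0.15 × 0.5 = 0.075 SD. Largest: 0.30 × 0.8 = 0.24 SD.
- Against an assumed true difference of 0.5 SD: 0.075/0.5 = 15% and 0.24/0.5 = 48%.
- If p1 = p0, the bias is 0.

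**4. Effect on the false-positive rate.** Suppose δ = 0, with n patients per group and a two-sided 5% test (normal approximation). The variance in each group is 1 + p(1 − p)d², and SE = √[(v1 + v0)/n]. The rejection probability is 1 − Φ(1.96 − bias/SE) + Φ(−1.96 − bias/SE).

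Example: n = 50, d = 0.8, p1 = 0.40, p0 = 0.20. Then v1 = 1 + 0.24 × 0.64 = 1.154, v0 = 1 + 0.16 × 0.64 = 1.102, SE = √(2.256/50) = 0.212, bias = 0.16, and the rejection probability is 11.7%.

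Over n = 20 to 50 per group, d = 0.5 to 1.0 and p0 = 20%, all assumed:

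| Imbalance p1 − p0 | Bias (SD) | False-positive rate |
|---|---|---|
| 0 points | 0 | 5% |
| 10 points | 0.05 to 0.10 | 5.3% to 7.4% |
| 20 points | 0.10 to 0.20 | 6.1% to 15.0% |
| 30 points | 0.15 to 0.30 | 7.5% to 27.7% |

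**5. Which lung measure to use.** Breathing reserve is 1 − peak VE/MVV. With the protocol's formula this is 1 − peak VE/(40 × FEV1). Peak VE (ventilation at peak exercise) is itself a CPET result, so selecting on breathing reserve selects partly on the outcome. FEV1 and FEV1/FVC are taken before exercise and do not have this problem.

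**The case against.** The strongest reply is that the Statistical Plan names no variables at all. A reader might infer that no planned comparison uses spirometry, but the text does not show this: lung function could be among the unnamed continuous variables, and the lack of detail is general. That stands. It does not rescue the plan, because none of the listed methods adjusts for anything, whichever variables go into them.

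Second, spirometry does have a stated use. MVV is the reference for respiratory reserve, and past medical history also reached the research team (Recruitment and informed consent). A ventilatory limit can therefore be recognised in a single test. A reader might infer that lung disease will be reported as a cardiac or non-cardiac pattern. The documents define no such patterns, and the workflow section describes only a preliminary report, so misreading is a risk and not a shown result. What remains is that no rule says what counts as limited or how such a patient enters the group comparison.

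Third, a reader might infer that lung patients gather in a group without heart failure and so hide a true cardiac difference. The plan does not say what the two groups are. With another split, or with lung disease commoner among patients with heart failure, the bias could vanish or inflate the difference.

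Finally, the Purpose text sits among lay material in the appendices and is not visibly tied to the Statistical Plan. The point does not need it: the spirometry subsection's own rationale is enough. Parts of the document were not available to this review, so formal objectives or group definitions there could not be checked.

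**Conclusion.** The concern holds in a limited form. Respiratory limitation is a recognised, measured and unexcluded influence on the CPET measures, and no listed analysis can take it out of the two-group comparisons. Confounding follows if its frequency differs between the groups, and only then. Direction and amount cannot be derived from the documents. The range of 0.075 to 0.24 SD (15 to 48% of an assumed 0.5 SD difference) rests wholly on assumed frequencies and shifts, and the bias is zero under balance. The documents do not support saying that results have been misattributed to the heart or that a true difference has been masked. This is a worthwhile and inexpensive improvement, not a flaw that invalidates the study.

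**What to change.** 1. Report FEV1, FEV1/FVC and breathing reserve by group. This shows whether there is an imbalance, and in which direction.
2. Repeat the group comparisons of the CPET measures adjusted for baseline spirometry, for example by linear regression on group plus FEV1/FVC or FEV1. Show adjusted and unadjusted estimates together: if the condition that defines the groups itself affects spirometry, adjustment would remove part of the difference of interest.
3. As a secondary sensitivity analysis, repeat the comparisons without patients who meet a stated definition of respiratory limitation. Base the definition mainly on resting spirometry, and note that breathing reserve depends on the CPET result.
4. Judge by how far the estimates and confidence intervals move from the unadjusted analysis, not by whether significance persists. The sensitivity set is smaller, so loss of significance may be only loss of power.
5. The Study Protocol section gives data collection as July 2024 to July 2025, and the Statistical Plan is in the past tense. Fix the definition before the repeat is run, and label the analysis post hoc if results are already known.

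The cost is slightly more analysis and fewer patients in the sensitivity set. No new test or visit is needed.

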#### **ii- Preparation phase:**

Gas and volume calibration was carried out. Patient details including age, biological sex, weight, height was entered in the CPET software. Calculation of Incremental workload protocol is done using the Wasserman's formula:

$$W = \underline{\text{PredVO2max}} - \underline{\text{VO2unloaded}}$$

The participant was asked to mount the cycle ergometer, and a facemask is attached covering the mouth and nose. The participant was instructed not to speak during the test and communicate only using hand movements to avoid artifacts. The disposable chest and limb electrodes were attached to the participant for ECG recording and a ear lobe pulse oximeter was attached.

### **Resting baseline**

The participant rested on the cycle ergometer without movement to record the baseline readings and minimize alterations caused by anxiety.

### **Unloaded cycling (warm-up)**

The participant was asked to pedal along for 3 minutes with the cycle ergometer unloaded. The participant was advised to keep the cadence (RPM) between 60 to 65 at all times of the test.

### **Increasing workload**

Lasting  $10 \pm 2$  minutes, this phase involved a gradual (ramped) increase in exercise intensity. The workload (resistance required to turn the flywheel) increased at a pre-defined/calculated rate for the duration that the patient was able to continue cycling. The patients were motivated to keep cycling while keeping the cadence above 55 rpm at all times. Blood pressure recordings at 2 minutes interval at the initial segment of the phase followed 1 minute interval once the respiratory exchange ratio was seen to cross 1.0 mark. The perceived exertion assessed via the Borg-10 scale was recorded at 4 minutes into the test and as close to maximal exhaustion as possible. The test was switched to recovery phase at the point where the patients raised their hand signaling, they were maximally exhausted.

### **Recovery**

The recovery phase lasted for 3-5 minutes during which the load on the bike was reduced to zero watts while patients continued to cycle at the same cadence. Serial BP readings were taken at every 2-minute intervals. The test was terminated once VO2 had returned to 50% of the peak values or the heart rate and systolic BP return to within the 20 beats/min and 20mm Hg of the pretest resting values respectively.

## **Post-CPET workflow analysis**

After the CPET is concluded and the patient has left, the CPET software is switched to workflow mode. In the workflow mode, the preliminary basic analysis is done as the software guides through different stages of the workflow mode. The peak values, ventilatory thresholds and the slopes are confirmed manually by adjusting the areas on the curved out of which the software identifies and reports those values. Once in place, the software generated a preliminary report that can be saved into the system.

[figure not shown]
## **Statistical Plan**

Data was analyzed using SPSSv29. Continuous variables were assessed for normality using the Shapiro-Wilk test and visual inspection of histograms and Q-Q plots. Normally distributed continuous variables are presented as mean  $\pm$  standard deviation (SD), while non-normally distributed variables are presented as median (interquartile range). Categorical variables are presented as frequencies and percentages.

For normally distributed continuous variables, independent samples t-tests were used to compare differences between two groups. For non-normally distributed continuous variables, the Mann-Whitney U test was applied. Categorical variables were analyzed using chi-square tests.

Relationships between continuous variables were examined using Pearson's correlation coefficient for normally distributed variables and Spearman's rank correlation for non-normally distributed variables. Statistical significance was set at  $p<0.05$  for all tests.

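### The Statistical Plan has only unadjusted two-group tests and pairwise correlations; age, sex and body size are recorded but not planned as adjustment covariates (minor, cheap to improve)

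*Combined protocol and SAP*

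**What the plan says.** All references are to the combined protocol and SAP.

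- **Statistical Plan.** "For normally distributed continuous variables, independent samples t-tests were used to compare differences between two groups". Non-normal variables go to the Mann-Whitney U test, categorical variables to chi-square, and associations to Pearson or Spearman correlation, all at p<0.05. The section contains no regression, analysis of covariance, partial correlation, stratification or matching. It names no outcome and does not define the two groups.
- **Study Protocol.** "The data collection for this cross-sectional study was conducted" from July 2024 to July 2025. No randomisation is described.
- **Inclusion Criteria.** "Males and females"; "Age ranged between 18 – 80 years"; "Clinical suspicion of heart failure with preserved ejection fraction".
- **Preparation phase.** "Patient details including age, biological sex, weight, height was entered in the CPET software". A predicted VO2max appears in the formula that sets the workload ramp.
- **Post-CPET workflow analysis.** "The peak values, ventilatory thresholds and the slopes are confirmed manually". Whether these are analysed as absolute, per-kg or percent-predicted values is not stated.
- **Spirometry.** "The MVV calculated is used as a reference for respiratory reserve during CPET". Lung function therefore already has a role in reading the test and is not part of this point.

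**The concern.** In an observational cohort with a wide age range and both sexes, nothing in the design makes two groups alike in age, sex or body size. If such a factor differs between the groups and is related to the CPET measure, the crude difference contains its contribution. A crude correlation between two measures that both vary with age contains a shared age component in the same way.

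What is at stake is interpretation. A crude result describes these patients correctly, but it cannot by itself support a reading that the group or the condition explains the difference. The variables needed to separate the two are already recorded.

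**Working it through.** **No figure to reproduce.** The documents give no sample size, SD, effect size, group definition or group imbalance. Everything below is an illustration on assumed inputs, apart from the two-sided reading of the plan's 5% level.

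**Assumed inputs.** Outcome slope 0.25 mL/kg/min per year of age (range 0.15 to 0.35); within-group outcome SD 5; within-group age SD 10 years; 30 per group (range 20 to 50); no group difference at equal age.

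**1. Crude two-group test.** Standardised difference d = slope × gap / 5. Non-centrality = d × √(n/2). The rejection rate comes from the non-central t distribution with 2n − 2 degrees of freedom. For n = 30 and slope 0.25:

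| Age gap (years) | Crude difference | d | Rejection rate |
|---|---|---|---|
| 1 | 0.25 | 0.05 | 5.4% |
| 2 | 0.50 | 0.10 | 6.7% |
| 3 | 0.75 | 0.15 | 8.8% |
| 5 | 1.25 | 0.25 | 15.9% |
| 10 | 2.50 | 0.50 | 47.8% |

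Over slopes 0.15 to 0.35, gaps of 1 to 3 years give 5.1% to 12.6%. Varying slope and n together, gaps of 5 to 10 years give 7.5% (n = 20, slope 0.15, 5 years) to 93% (n = 50, slope 0.35, 10 years).

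**2. Adjusted test.** With age in the model, simulation (20,000 runs, n = 30 per group, slope 0.25) rejects in 4.9% to 5.3% of studies for gaps of 1 to 10 years. With age, sex and body size in the model, a simulation at a five-year gap rejects in about 5%.

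**3. Percent-predicted outcome.** If the scale removes the whole age slope, the crude rate is 5% at any gap. If one fifth of the slope remains (0.05 per year), d is 0.05 at 5 years and 0.10 at 10 years, giving 5.4% and 6.7%.

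**4. Correlations.** Take two variables related only through age, n = 60. Each correlates r with age, so the crude correlation is r × r, for example 0.3 × 0.3 = 0.09. For r = 0.1, 0.2, 0.3, 0.5 and 0.7, the crude test rejects in 5.0%, 6.1%, 10.6%, 48.9% and 98.3% of simulated studies. The partial correlation given age rejects in 5.0% to 5.2%.

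**5. Effect on precision.** Ignoring the lost degrees of freedom, adjusted SE / crude SE = √[(1 − R²y)/(1 − R²g)], where R²y = (slope × 10/5)² and R²g = 0.25 × gap² / (100 + 0.25 × gap²).

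- Slope 0.25, gap 5: √(0.75/0.941) = 0.893, so the SE is 11% lower.
- Slope 0.25, gap 10: √(0.75/0.80) = 0.968, 3% lower.
- Slope 0.15, gap 10: √(0.91/0.80) = 1.067, 7% higher.
- Slope 0.05 (one fifth remaining), gaps 5 and 10: 1.026 and 1.112, 3% and 11% higher.

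In the simulation with age, sex and body size at a five-year gap, the SE was about 8% lower than the crude one.

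**The case against.** The strongest reply is that the main gap lies upstream. Until the two groups, the outcomes and their scale are named, adjustment could be needed, redundant or unhelpful. This stands. It is why naming them comes first in the fix, and why covariates that define the groups or are built into the outcome must be left out.

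A second reply is that part of the adjustment may already exist, since a predicted VO2max is obtained. This stands in part. The protocol uses that value only to set the ramp; it neither states nor excludes a percent-predicted analysis scale.

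A third is that nothing in the plan depends on adjustment. The Statistical Plan undertakes only to compare and to examine relationships. The one explanatory aim, concerning the heart condition and what causes the symptoms, is in leaflet-like appendix text under Purpose. This also stands and lowers the weight of the point. The descriptive aim of showing how patients respond to the test is unaffected.

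Two stronger readings are tempting. A reader might infer that age, sex and body size take part in no planned comparison at all. The text does not support that: the Statistical Plan names no variables, so these could well be compared between groups or correlated as descriptors. What is absent is their use for adjustment. A reader might also infer that the study's results are confounded, or that its t-tests exceed their 5% error rate. The documents give no data or imbalance to show the first. As to the second, in the scenarios above the crude means really do differ, so the rejections are not errors of the test.

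**Conclusion.** The point holds as a minor one. The plan contains only unadjusted analyses of a non-randomised cohort of both sexes aged 18 to 80, and the recorded age, sex, weight and height are not planned as adjustment covariates. Crude differences or correlations on absolute or per-kg scales could partly reflect them.

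The size for this study is unknown. On the assumed inputs it is slight for age gaps of 1 to 3 years and can be large for 5 to 10 years, but the joint range of 7.5% to 93% is too wide to size the effect here, and nothing in the documents indicates which gap applies. A percent-predicted outcome would remove much of the problem. The conclusion rests on the content of the Statistical Plan and the design, not on any one scenario.

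**What to change.** 1. Name the two groups, the key CPET outcomes and the scale of each.
2. Beside each crude result for those outcomes, report a linear model with group, age, sex and, where appropriate, body size, giving the adjusted difference and its 95% confidence interval.
3. For associations, add regression or partial correlations given age and sex.
4. Omit any covariate that defines the groups or is built into the outcome: age, sex and size for percent-predicted values, weight for per-kg values.
5. Where body size is used, show results with and without it, because weight could be linked to the condition itself.
6. Keep the model short for the achieved sample size.
7. Describe the crude results as unadjusted associations. Label the adjusted analyses post hoc if the crude ones have been run, which is likely: data collection ran to July 2025 and the analysis methods are described in the past tense.

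The cost is some plan wording and a few extra models in SPSS, with no new data. The downside is a few degrees of freedom and somewhat wider intervals when a covariate is only weakly related to the outcome but imbalanced between the groups.

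### Does the plan need to name the Welch form of the two-group t-test and give a rule for unequal variances?

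*Combined protocol and SAP*

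**What the plan says.** The Statistical Plan names the software, "Data was analyzed using SPSSv29", and one assumption check: "Continuous variables were assessed for normality using the Shapiro-Wilk test and visual inspection of histograms and Q-Q plots". The two-group test then depends on that check. The rule for one branch is "For normally distributed continuous variables, independent samples t-tests were used to compare differences between two groups"; for the other, "For non-normally distributed continuous variables, the Mann-Whitney U test was applied". The threshold is common to all: "Statistical significance was set at $p<0.05$ for all tests".

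The section does not name the pooled or the Welch form, a test of equal variances, or a rule for unequal variances. The supplied text does not define the two groups and gives no group sizes or SDs. Some pages and figures are not in the supplied text, so their absence is not counted against the plan. The Study Protocol section describes the design as cross-sectional: "The data collection for this cross-sectional study was conducted at the Cardiology department of Ulster hospital between July 2024 to July 2025". Nothing in the visible text fixes the ratio of the group sizes.

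**The concern.** The name of the test does not identify a single p-value. SPSS offers one result that assumes equal variances and one that does not, and the two can fall on opposite sides of 0.05. In a cross-sectional study without randomisation or matching in the visible text, the groups may well differ in size.

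The pooled test tolerates unequal variances only when the groups are of similar size. If the smaller group is the more variable one, the pooled p-value is too small and false positives rise. If the smaller group is the less variable one, the p-value is too large and real differences are missed. An unstated choice could also, in principle, be made after both p-values have been seen. Naming Welch in one sentence would close the question at little cost.

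**Working it through.** **Inputs from the documents.** Nominal alpha 0.05; independent samples t-test for normal variables; normality the only check named. There is no sample size, SD or power figure to reproduce.

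**Assumptions.** Two-sided tests, normal data, no true difference, total of 60 split 30/30, 40/20 or 45/15, and SD ratio r (smaller group over larger) from 0.5 to 2.

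**Step 1: why the pooled test drifts.** Let the larger group have size n1 and SD 1, and the smaller group size n2 and SD r.

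- True variance of the mean difference: T = 1/n1 + r²/n2.
- Variance the pooled test expects on average: P = [((n1−1) + (n2−1)r²)/(n1+n2−2)] × (1/n1 + 1/n2).
- With 58 degrees of freedom the critical value is 2.0017. The effective critical value is roughly 2.0017/√(T/P), and its two-sided t tail (58 df) approximates the true error rate.

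Putting in the numbers:

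- 30/30, r = 2: T = 1/30 + 4/30 = 0.1667; P = 2.5 × 0.0667 = 0.1667; T/P = 1. Error about 5.0%.
- 40/20, r = 2: T = 0.025 + 0.2 = 0.225; P = (115/58) × 0.075 = 0.1487; T/P = 1.513; 2.0017/1.2301 = 1.627. Error about 10.9%.
- 45/15, r = 2: T = 0.0222 + 0.2667 = 0.2889; P = (100/58) × 0.0889 = 0.1533; T/P = 1.885; 2.0017/1.3730 = 1.458. Error about 15.0%.
- 40/20, r = 0.5: T = 0.0375; P = (43.75/58) × 0.075 = 0.0566; T/P = 0.663; 2.0017/0.8142 = 2.459. Error about 1.7%.
- 45/15, r = 0.5: T = 0.0389; P = (47.5/58) × 0.0889 = 0.0728; T/P = 0.534; 2.0017/0.7309 = 2.739. Error about 0.8%.

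**Step 2: simulation.** With 400,000 simulated datasets per cell (Monte Carlo standard error about 0.03 points), the ranges over r = 0.5 to 2 are:

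| Split | Pooled | Welch | Form chosen by a variance-ratio F test at 0.05 |
|---|---|---|---|
| 30/30 | 5.0–5.2% | 5.0% | 5.0% |
| 40/20 | 1.8–11.1% | 5.0% | 4.2–6.2% |
| 45/15 | 0.8–15.3% | 5.0–5.1% | 3.8–7.2% |

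A separate run with the mean-based Levene test itself, at r = 1.25 to 2, gave 5.4–6.4% at 40/20 and 6.4–7.6% at 45/15.

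**Step 3: what must be true for harm.** The pooled result must be the one reported, the group sizes must differ, and the variances must differ. The documents show none of the three. The 15.3% figure needs a 3:1 split, a twofold SD ratio in the unfavourable direction, and an analyst who ignores any sign of unequal variances.

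**Step 4: how far Welch is a guarantee.** Welch holds at 5.0–5.2% when each group has 10 or more. It runs at 4.4–5.8% when the smaller group has 5, 6.3–7.8% at 57/3, and up to 12.7% with a group of 2. Because the documents give no group sizes, naming Welch could not by itself secure 5% in every case.

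**The case for a change.** The strongest argument for a change is that the omission is real and visible. The paragraph on test selection is complete, so removed pages do not explain it. The pooled error rates agree across separate simulations and with the approximation above. Letting Levene's test choose the form does not fully repair them, because that test often misses a real difference: at 45/15 it rejects in only 17% of datasets at SD ratio 1.25 and 44% at 1.5. Nor does the normality screen: at 45/15, among datasets sent to the t-test, the pooled form still rejects in 9.5% to 14.8% at SD ratios of 1.5 and 2. Welch costs little when variances are equal: about 2 points of power at 45/15 (80.0% to 78.0%) and under 1 point at 40/20 (80.1% to 79.3%).

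The arithmetic stands, and Welch is a sensible default. What does not follow is that the plan is wrong. Its wording permits Welch, and if that result was read the t-test branch is sound. Under the Levene-guided choice, the excess over 5% is at most about 2.6 points in the assumed splits (7.6% against 5.0%). The risk of choosing a form after seeing both p-values exists, but nothing in the documents suggests that it happened.

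**Conclusion.** No change to the plan is needed. The form of the t-test is a missing detail in a general test-selection paragraph, and an analyst can fill it soundly within the words as they stand. The pooled form would be materially off only if it was reported and both sizes and variances differed: about 1% to 15% under the assumed 40/20 and 45/15 splits with SD ratios of 0.5 to 2, against 5.0–5.2% with equal groups. All these figures rest on assumed group sizes, assumed SD ratios and normal data, and none shows an error in this study. The analysis is described in the past tense, so the useful step belongs to reporting: the report may say which form was used and, if it was the pooled one, show the Welch result beside it.
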